# Sample size calculation

For the calculation of the sample size, the case of previous studies that explored this same relationship will be taken as the basis, using the following formula:

$$n = (N) (Z_{\alpha/2})_2 (p)(q) / (N-1) (E)_2 + (Z_{\alpha/2})_2 (p)(q)$$

# Where

- N = total infected population in Mexico (8463) Source: SISVER, SINAVE, DGE, SSA, May 12, 2020.
- $\mathbf{Z}_{\alpha/2} = 95\%$  bilateral confidence level (1.96)
- p = 50% success rate (0.5)

- q = 50% failure rate (0.5)
- E = 5% error range (0.05)

#### Substituting the values

 $n = (8463) (1.96)_2 (0.5) (0.5) / (8463 - 1) (0.05)_2 + (1.96)_2 (0.5) (0.5)$ 

n = 368 patients.

#### Statistical analysis

Descriptive statistics, measures of central tendency, measures of dispersion and standard deviation will be used.

While for the qualitative variable's frequency measures (relative, absolute and percentage) were used. Relative risk will be performed with a 95% confidence interval of significance (95% CI) and contingency tables.

For inferential statistics, the difference in proportions between the dependent (orotracheal intubation) and independent (prone position) variables will first be verified based on the number of expected observations (<5) Fisher's exact test or (> 5) Chi square test, contrasting H0:  $\phi = 1$ , taking p <0.05 as a statistically significant value.

A multivariate analysis will be used to generate linear regression models with the different variables: prone time, age, gender and orotracheal intubation, SpO2 / FiO2 index in order to explain their interactions (if the time in prone, age or gender affects the main objective) as well as adopting the best model that matches the observations (best R2, AIC) as a predictive model.

The results will be presented in graphs and / or tables as appropriate.

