# Objective

#### Main objective

To analyze the relationship between the awaken prone positioning and the need for orotracheal intubation.

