#### Dependent

Variable	Conceptual definition	Operational definition	Туре	Measurement scale
Orotracheal intubation	Placing a probe into the trachea through the mouth or nose to connect to a mechanical ventilator.	Performing intubation for any cause or non- intubation during your hospitalization.	Qualitative	Nominal (dichotomous): Yes No

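### The only multivariable model named is linear regression, yet intubation is Yes/No: name each model's response and use a binary-outcome model for intubation

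*Protocol*

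**What the plan says.** The main objective is stated as "To analyze the relationship between the awaken prone positioning and the need for orotracheal intubation". The table of dependent variables defines the outcome as "Performing intubation for any cause or non- intubation during your hospitalization" and gives its scale as "Nominal (dichotomous): Yes No".

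The Statistical analysis section then takes two steps.

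- Crude comparison: "the difference in proportions between the dependent (orotracheal intubation) and independent (prone position) variables will first be verified", by chi-square or Fisher's exact test. For the effect measure, "Relative risk will be performed with a 95% confidence interval of significance (95% CI) and contingency tables".
- Modelling: "A multivariate analysis will be used to generate linear regression models with the different variables: prone time, age, gender and orotracheal intubation". The list ends with the SpO2/FiO2 index. The purpose is given as "in order to explain their interactions (if the time in prone, age or gender affects the main objective", and the section ends the modelling step by "adopting the best model that matches the observations (best R2, AIC) as a predictive model".

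The protocol names no logistic, log-binomial, Poisson or other binary-outcome model. The modelling sentence does not say which listed variable is the response.

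**The concern.** The protocol itself fixes the method, so this is not a detail left to a statistical analysis plan. If intubation is the response, the stated form fits the outcome badly in four ways.

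- The variance of a 0/1 outcome changes with its mean, and no robust standard errors are specified.
- Fitted risks can fall outside 0 to 1, which matters for a model meant for prediction.
- R2 is a poor fit measure for a 0/1 outcome.
- Interactions are tested on the risk-difference scale, while the reported effect measure is a relative risk.

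This is a retrospective cohort, and the contingency-table relative risk is unadjusted. The regression is the only planned step that could adjust the main association or examine how age and gender bear on it.

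**Working it through.** **Which variable is the response?** The modelling sentence asks what affects the main objective. The main objective concerns intubation, and intubation is the only variable in the protocol's table of dependent variables. On that purpose the response is intubation. The SpO2/FiO2 index, also in the list, belongs to a specific objective, and linear regression would suit it.

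**The plan's own figure.** The stated sample size is used below as the size of each simulated study. With N = 8463, Z = 1.96, p = q = 0.5 and E = 0.05:

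n = 8463 × 3.8416 × 0.25 / (8462 × 0.0025 + 3.8416 × 0.25) = 8127.87 / 22.1154 = 367.5, so 368 as stated.

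**Variance.** For a 0/1 outcome the variance is p(1 − p). At assumed risks of 12% and 75% this is 0.1056 and 0.1875, a ratio of about 1.8.

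**Fitted risks outside 0 to 1.** The check simulates studies of 368 from a logistic truth and fits ordinary least squares on age, sex, prone hours and SpO2/FiO2. The protocol's background cites one COVID-19 emergency series in which 64% avoided intubation, hence 36% intubated. All other inputs are assumptions: age SD 14 years, SpO2/FiO2 SD 60, half proned. Log-odds effects per 10 years, per 50 SpO2/FiO2 units and per 5 prone hours are:

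- weak: 0.2, −0.2, −0.1
- moderate: 0.4, −0.6, −0.2
- strong: 0.6, −1.0, −0.3

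| Intubated | Weak | Moderate | Strong |
|---|---|---|---|
| 10% | 1.8% | 10.6% | 18.2% |
| 36% | 0.07% | 3.0% | 8.3% |
| 50% | 0% | 1.5% | 6.3% |

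Entries are the mean share of patients with an impossible fitted risk. At 36% intubated, 15% of studies have at least one such patient with weak predictors and 99% with moderate ones. A separate simulation at about 34% intubated gave 6.7%. Models with only prone, age and their product gave about 0% (untreated risk 30% to 50%) to 3% (12% to 75%).

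**Interaction scale.** With untreated risk p0 and a constant relative risk RR, the risk difference is p0 × (RR − 1). For RR = 0.6:

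- p0 = 20%: 0.20 × (−0.4) = −8 points
- p0 = 60%: 0.60 × (−0.4) = −24 points

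The linear model therefore carries an interaction of −16 points where the relative risk has none. Over RR 0.5 to 0.8 and untreated risks of 20/60, 10/50 and 30/50%, it runs from −4 to −20 points.

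The reverse also holds. A constant difference of −15 points on untreated risks of 25% and 75% gives relative risks of 10/25 = 0.40 and 60/75 = 0.80.

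**How often each scale flags an interaction** (two-sided 0.05, n = 368, half proned, all risks assumed):

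| Truth | Linear | Log relative risk |
|---|---|---|
| Constant RR, continuous age: from RR 0.8 with untreated risk 12–75%, or RR 0.6 with 30–50%, up to RR 0.6 with 12–75% | 8% to 33% | about 5% |
| Constant RR 0.5 / 0.6 / 0.7, two strata at 20% and 60% | 63 / 43 / 25% | 4 / 5 / 4% |
| Constant RR 0.5 / 0.6 / 0.7, two strata at 10% and 50% | 69 / 51 / 32% | 3 / 3 / 3% |
| Constant difference of −15 to −18 points, untreated risk about 20–25% rising to 75% | 2% to 4% | 21% to 27% |

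The continuous-age rows run over ages 30 to 80 and use modified Poisson with robust standard errors for the log scale.

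**The case against.** The strongest defence has four parts.

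- **The response is not stated.** SpO2/FiO2 is in the list, and a linear model would suit it. This stands in part: the certain defect is that the response is unnamed. Yet if SpO2/FiO2 was meant, the sentence still needs correcting, and the main objective would have no multivariable model at all.
- **A linear model for a binary outcome can be legitimate.** With robust standard errors it estimates adjusted risk differences. That is true, but the protocol states neither a risk-difference target nor robust errors, and it reports a relative risk.
- **Interaction depends on scale.** This stands in full. A reader might infer that the linear model's interactions are false. The protocol does not support that, because it does not say on which scale the effect is expected to be constant, and it also refers to a difference in proportions. Under a constant difference, the model proposed here is the one that flags interactions.
- **The main comparison comes first and is separate.** This also stands. A reader might infer that the main result is invalid, but the chi-square or Fisher test and the crude relative risk do not depend on the regression.

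A reader might also infer that impossible risks are certain. They are possible, and with weak predictors near 50% risk they are rare.

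**Conclusion.** The point holds as a mismatch between a stated method and its outcome, on the reading that intubation is the response. Ordinary linear regression is named for a Yes/No outcome without robust standard errors, partly selected by R2, and meant for prediction.

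The size depends on assumptions that the protocol cannot settle. Impossible fitted risks affect about 0% to 8% of patients at 34–36% intubated, and up to 18% at 10% intubated with strong predictors. Under a constant relative risk, the linear scale flags an interaction in about 8% to 33% of studies with continuous age, and up to 69% in the more extreme two-stratum cases. The interaction simulations treat proning as Yes/No, whereas the plan's model uses prone time, so they illustrate the mechanism and do not forecast this study's result.

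This should be fixed before analysis. It falls short of an essential correction because the crude test and relative risk stand, and because the data already planned would serve the corrected model.

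**What to change.** In the Statistical analysis section:

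- Name the response of each model.
- For intubation, replace linear regression by log-binomial or modified Poisson regression with robust standard errors, giving adjusted relative risks with 95% CI to match the reported relative risk. Logistic regression is acceptable for prediction, but its interactions are on the odds scale, and the text should say so.
- State the scale on which interactions are judged, and test them as product terms in that model.
- Select by AIC, or another fit measure suited to the chosen model, rather than by R2.
- Keep linear regression for the continuous SpO2/FiO2 index.

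The cost is a sentence or two of wording. The data, the sample size of 368 and the crude analysis do not change, and standard software suffices.

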# Independent variable

Variable	Conceptual definition	Operational definition	Туре	Measurement scale (years)	
Age	Time elapsed from the birth of a person to a certain moment.	The age recorded in the clinical record at the patient's admission to the hospital will be considered.	Discrete quantitative	
 
18 a 27
 
28 a 37
 
38 a 47
 
48 a 57
 
58 a 67
 
68 a 77
 
78 a 87
 
88 a 97
 
997
 
	
Gender	Social concepts of functions, behaviors, activities and attributes for men and women.	Gender that is registered in the clinical record	Qualitative nominal	Male Female	
Prone position	What is called the prone position	Record in the record of the placement of the patient in the prone position for a minimum of 2 hours.	Qualitative	Nominal (dichotomous): Yes No	
Type of oxygen support supplied	Device used for supplemental oxygen administration.	Record in the clinical record of the type of oxygen supplied.	Qualitative nominal	
 
Nasal cannulas
 
High flow nasal cannulas
 
Face mask
 
Other
 
	
Partial oxygen saturation index (SpO2) / inspired oxygen fraction (FiO2)	Resulting index for SpO2 / FiO2 ratio	2 index records will be taken at admission and the second after the patient's prone position, recorded in the clinical record.	Discrete quantitative	1. 100 a 150 2. 151 a 200 3. 201 a 250 4. 251 a 300 5. 301 a 350	

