# Confusing variables

Variable	Conceptual definition	Operational definition	Туре	Measurement scale
Comorbidities	Presence of one or more disorders in addition to the primary disease or disorder	Registration in the clinical record of any of the comorbidities described.	Qualitative nominal	
 
1 Diabetes mellitus
 
2 Systemic arterial hypertension
 
3 Chronic obstructive pulmonary disease
 
4 Obesity
 
5 Chronic kidney disease
 
6 Ischemic heart disease
 
7 Other heart diseases
 
8 Other diseases
 

Pharmacotherapy		Registration in the clinical record of the described management.	Qualitative nominal	
 
Antivirals
 
Hydroxychloroquine
 
Antibiotics
 
Corticosteroids
 
Immunomodulators
 
Others
 

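### Prone yes/no is tested against intubation only without adjustment, and the one multivariable model lists neither that exposure nor the two confounders the protocol names

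*Protocol*

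**What the plan says.** The Protocol's main objective is "To analyze the relationship between the awaken prone positioning and the need for orotracheal intubation". The design is an observational, retrospective cohort (Methodology).

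The exposure is dichotomous and is defined in the *Independent variable* table as "Record in the record of the placement of the patient in the prone position for a minimum of 2 hours". The outcome, intubation during the hospital stay, is also yes/no (*Dependent* table).

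The *Confusing variables* table holds two entries: comorbidities ("Registration in the clinical record of any of the comorbidities described") and pharmacotherapy ("Registration in the clinical record of the described management"). Type of oxygen support is listed separately, among the independent variables ("Record in the clinical record of the type of oxygen supplied").

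The *Statistical analysis* section plans two things that bear on the main objective:

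- a relative risk with 95% CI from contingency tables, and a chi-square or Fisher test of prone position against intubation at p < 0.05, with no adjustment or stratification stated;
- "linear regression models with the different variables: prone time, age, gender and orotracheal intubation, SpO2 / FiO2 index", meant to show "if the time in prone, age or gender affects the main objective", followed by "adopting the best model that matches the observations (best R2, AIC) as a predictive model".

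**The concern.** Nobody was randomised to prone position, so proned and non-proned patients may differ in ways that also affect intubation. The protocol recognises this by naming two confounders, and its data form collects both. It then assigns neither to any comparison of prone with non-prone patients. The Problem statement describes several comorbidities as common in Mexico and linked to death (it does not mention intubation).

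If the groups differ in these factors, the crude relative risk mixes that difference with any effect of proning. An apparent benefit or harm could then be confounding. This affects the main objective and the test of the null hypothesis. The Ethical considerations also say that the study is meant to encourage use of awake proning.

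**Working it through.** **1. What each planned analysis contains**

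| Variable | Role in the Protocol | On the data form | Crude RR and test | Listed for the linear models |
|---|---|---|---|---|
| Prone yes/no | Exposure | Yes | Yes | No |
| Prone time (hours) | Not in the variable tables | Yes | No | Yes |
| Age, gender, SpO2/FiO2 | Independent variables | Yes (index labelled SaO2/FiO2) | No | Yes |
| Comorbidities | Confounder | Yes | No | No |
| Pharmacotherapy | Confounder | Yes | No | No |
| Type of oxygen support | Independent variable | Yes | No | No |

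Prone time could stand in for the exposure if non-proned patients were coded 0 hours, but the Protocol does not say so. Both named confounders would still be missing.

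**2. The plan's own sample size** (*Sample size calculation*)

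n = N z² p q / [(N − 1) E² + z² p q], with N = 8463, z = 1.96, p = q = 0.5, E = 0.05:

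8127.87 / (21.155 + 0.9604) = 367.52, rounded up to 368.

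The stated figure reproduces. It is not in dispute and is used below.

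**3. Possible bias in the crude relative risk**

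The documents give no prevalence or strength for any confounder, so these inputs are assumptions. For one omitted binary factor with relative risk R for intubation, present in a share p1 of prone and p0 of non-prone patients, and no true prone effect:

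crude RR = [1 + p1(R − 1)] / [1 + p0(R − 1)]

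| p1 vs p0 | R = 1.5 | R = 2 | R = 3 |
|---|---|---|---|
| 30% vs 50% | 1.15/1.25 = 0.92 | 1.3/1.5 = 0.87 | 1.6/2.0 = 0.80 |
| 50% vs 30% | 1.25/1.15 = 1.09 | 1.5/1.3 = 1.15 | 2.0/1.6 = 1.25 |
| 40% vs 50% | 1.2/1.25 = 0.96 | 1.4/1.5 = 0.93 | 1.8/2.0 = 0.90 |

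**4. False rejection by the planned test**

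Simulation with n = 368, no prone effect, 40% or 60% of patients proned, and chi-square without continuity correction at 0.05:

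| Imbalance | Intubated overall | R = 1.5 | R = 2 | R = 3 |
|---|---|---|---|---|
| 30% vs 50%, either direction | 30-40% | 8-10% | 13-20% | 26-42% |
| 30% vs 50%, either direction | 20% | 7% | 9-11% | 16-19% |
| 40% vs 50% | 30-40% | 5-7% | 7-9% | 10-13% |

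A normal approximation with 184 patients per group and 40% intubated among the non-proned agrees for 30% vs 50%: 9.7%, 18.4% and 35.9%. With the factor included in a robust Poisson model, false rejection returns to about 4-6%.

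**5. Can 368 patients support an adjusted model?**

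The Protocol gives no expected intubation rate. Two assumed rates are used:

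- 36%: 0.36 × 368 ≈ 132 events. This is the complement of the 64% in whom intubation was avoided in one series of proned patients cited in the Theoretical framework. Those patients had saturation below 90%, whereas this cohort takes any hospitalised patient.
- 20%: 0.20 × 368 ≈ 74 events.

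The core model has 6 parameters: prone 1, age 1, gender 1, SpO2/FiO2 1, comorbidity count (0, 1, 2+) 2.

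| Model | Parameters | Events each (132) | Events each (74) |
|---|---|---|---|
| Core | 6 | 22.0 | 12.3 |
| + oxygen support (3) | 9 | 14.7 | 8.2 |
| + drugs (6) | 12 | 11.0 | 6.2 |
| + both | 15 | 8.8 | 4.9 |

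With the Protocol's bands for age (8 terms) and SpO2/FiO2 (4 terms), the full model has 1 + 8 + 1 + 4 + 2 + 3 + 6 = 25 parameters, or 132/25 = 5.3 events each. Entering all eight comorbidities separately makes 31, or 4.3 each.

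**The case against.** **The plan does adjust.** The main objective speaks of prone positioning in general. The linear models include prone time with age, gender and SpO2/FiO2, the last a marker of severity. This stands in part: the plan is not free of covariates. But prone time is not tied to the defined exposure, and neither named confounder is listed. Selection on R2 or AIC may also drop covariates that are listed.

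**The covariate set may belong to an SAP that is not shown.** That would answer silence. Here the Protocol writes out the variables, the purpose and the selection rule, and its list conflicts with its own variable tables.

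**The illustration is invented and measures the wrong gap.** It sets the crude test against a model with one assumed factor. It does not set the planned covariates against the same set plus comorbidities and drugs. That is fair as a limit on what the figures show. They describe the only analysis planned for prone yes/no, and the top of the range needs a strong, clearly unbalanced factor.

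**Drugs and oxygen support may follow proning.** This is correct, since the form records no timing for either. It is a reason to keep them out of the main model, but it does not excuse omitting comorbidities.

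**Conclusion.** The concern holds, and the section should be corrected before analysis. That no estimate for prone yes/no is adjusted for the named confounders follows from the text alone and needs no assumption.

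The size of the bias cannot be known from the documents. On the assumed values it runs from negligible (relative risk 0.96 and 5-7% false rejection for a weak factor with a 10-point imbalance) to serious (0.80 or 1.25 and 26-42% for a factor with relative risk 3, a 20-point imbalance and 30-40% intubated). Adjustment would not remove confounding by factors that were not recorded, but omitting factors already named and collected is avoidable.

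**What to change.** In *Statistical analysis*, add one prespecified model for intubation yes/no. Modified Poisson regression with robust standard errors matches the planned relative risk; logistic regression would also serve.

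- **Main adjusted estimate.** Force in prone yes/no as defined in the *Independent variable* table, age and admission SpO2/FiO2 as continuous terms, gender, and comorbidities (for example a count of 0, 1, 2+). Report it with its 95% CI beside the crude relative risk.
- **Sensitivity analyses.** Show the same estimate with pharmacotherapy added and with oxygen support added, since both are untimed and may follow exposure.
- **Selection.** Do not apply R2 or AIC to this estimate; keep them for the predictive model.

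**Cost.** This is a rewording. Exposure, outcome and covariates are already on the form, although age and SpO2/FiO2 must be kept as recorded values and not only in the Protocol's bands. The confidence interval may widen. Model size is limited, most of all if intubation is nearer 20%, and a comorbidity count merges unlike conditions, so some confounding may remain. Restricting drugs or oxygen support to those started before proning would need extra form fields.

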# **Specific objectives**

To explore the impact of the awaken prone positioning on the partial oxygen saturation / inspired oxygen fraction index (SaO2 / FiO2).

Determine the free hours without the need for orotracheal intubation of patients in the awaken prone positioning.

To describe the characteristics of the patients in need of orotracheal intubation who were in the awaken prone positioning and those who were not.

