#### Information gathering instrument

Case	Gender	Age	Comorbidities	Type of oxygen support supplied	Pharmacotherapy	Awake prone position (Yes/no)	Time of Awake prone position (hours)	Initial SaO2/FiO2	SaO2/FiO2 before to the prone position	Prone position (hours)	Intubation Yes/No

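### Prone time has no stated window; read as cumulative hours it is cut short by intubation, which biases the dose model toward apparent benefit.

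*Protocol*

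**What the plan says.** The Statistical analysis section plans "linear regression models with the different variables: prone time, age, gender and orotracheal intubation, SpO2 / FiO2 index". The stated purpose is to see "if the time in prone, age or gender affects the main objective", and the main objective is the relation between awake proning and intubation. The model with the best R2 and AIC is then adopted for prediction.

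The outcome, in the Dependent variable table, is "Performing intubation for any cause or non- intubation during your hospitalization". It covers the whole stay. The yes/no exposure, in the Independent variable table, is "placement of the patient in the prone position for a minimum of 2 hours", also with no time window.

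The Information gathering instrument has a column "Time of Awake prone position (hours") and, three columns later, another headed with only "prone position (hours"). The Statistical analysis section does not say which one is prone time. The form has no field for the date or time of admission, first proning, intubation or discharge, although one specific objective is to "Determine the free hours without the need for orotracheal intubation of patients in the awaken prone positioning".

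**The concern.** Awake proning ends at intubation. A patient intubated on the first day cannot accumulate the hours of a patient who is proned for several days and never intubated. If the dose is the hours accumulated over the stay, short dose is partly a consequence of intubation, and a plain regression reads it as a cause. The plan sets no landmark, per-day rate, time-varying exposure or time-to-event model that would prevent this.

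Two features add to it. Selection by R2 and AIC favours a variable that partly encodes the outcome, and such a variable is complete only once the outcome is known, so it cannot serve for prediction. And because the form holds no times, the data as collected could not support a repair at the analysis stage.

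This is the only dose analysis planned. The Ethical considerations section says the work is meant to encourage use of awake proning, so a built-in lean toward benefit matters.

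**Working it through.** **The plan's own figure.** The sample-size formula, with its denominator bracketed, gives 8463 × 1.96² × 0.25 / (8462 × 0.05² + 1.96² × 0.25) = 8127.87 / 22.115 = 367.5, rounded up to 368. This reproduces. It is a precision calculation for one proportion and does not bear on the dose model.

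**Inputs from the protocol.** Significance as "taking p <0.05 as a statistically significant value"; n = 368; a minimum of 2 prone hours; intubation counted over the whole stay.

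**Assumptions, not in the protocol.** Half the patients proned (368 / 2 = 184). Intubation risk R of 30%, 40% or 50%. Constant hazard over 5 days, λ = −ln(1 − R)/5 per day. Prone rate of 4-12 h per day, unrelated to risk. No effect of proning.

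**Check 1: proned patients only.** Prone hours accrue until intubation or the end of the course. Intubation is regressed linearly on hours, 2,000 runs per cell, at least 2 h required. Share of runs with a significant negative slope (nominal about 2.5%), across the three risks:

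| How hours accrue | False significant benefit |
|---|---|
| One session of 2-3 h | about 3% |
| One session of 2-12 h | 6% to 7% |
| Day 1 only, 4-12 h/day | about 30% (24% to 34%) |
| 2-day course | 90% to 98% |
| 5-day course | 100% |

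For the 5-day course at 40% risk, without the 2-hour minimum, 66% are intubated below the median of total hours and 14% above it, with no true effect. For the single 2-3 h session the split is 39.7% against 39.3%.

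**Check 2: all 368 patients, non-proned at 0 h, age and sex in the model.** Further assumptions: about 8 prone hours per day, mean time to intubation 24 to 96 h, mean stay 8 days if not intubated.
- Proning continued to intubation or discharge, no confounding, intubation rate 20% to 50%: false significant benefit in 85% to 100% of runs.
- Proning often stopped earlier for unrelated reasons (mean 24, 48 or 72 h), intubation rate 36%: 45%, 86% and 97%.
- Early stopping, with sicker patients both proned and intubated more often (log-odds 1.0 per SD): about 0% to 56%.
- Log-odds 1.5 with stopping at a mean of 24 h: the sign reverses, significantly positive in 12% to 45%.
- Restricted to proned patients, the mean slope stayed negative in every cumulative-hours scenario, significantly so in 8% to 100% of runs.

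SpO2/FiO2 was not in this simulated model. Adjusting for it could remove part of the confounding and leave the truncation bias more exposed.

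**Check 3: the remedy.** With hours measured in the first 24 h, among proned patients un-intubated at 24 h and with later intubation as the outcome, the two-sided rejection rate returns to about 5%. Expected losses to the window are 184 × [1 − (1 − R)^(1/5)]: 12.7 at 30% risk, 17.9 at 40% and 23.8 at 50%. So about 160 to 171 of 184 remain.

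**The case against.** The strongest reply is that the protocol never calls the dose total or cumulative. It says only prone time, in hours. The durations it does give are on the scale of a session: the 2-hour minimum, and 30-120 minutes up to 2-3 hours in the studies it cites. For one short session there is essentially no bias, and a per-day or per-session dose would not carry it either. This stands as a limit on size. It does not remove the point: one hours field per patient, set against an outcome over the whole stay, is most naturally filled with the hours accumulated, and the form collects nothing from which to derive a daily rate.

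A reader might infer that the model is bound to show a benefit. The documents do not support that. The model is not restricted to proned patients, and with non-proned patients at 0 h confounding by severity can offset or reverse the sign.

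A reader might also infer that the second hours column holds proning on the ventilator, after the outcome. Nothing says so, and the column may be a translation or table-reading artefact. The supportable point is that the two columns are not told apart.

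Finally, the hypotheses are tested on yes/no proning by chi-square or Fisher's exact test, and the dose model is secondary. That is correct and lowers the severity. The exact definition of a covariate can be left to an analysis plan. Here, though, the protocol itself fixes the model, its purpose and a form without times, so a later plan would lack the data to correct it.

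**Conclusion.** The concern holds in conditional form. Prone time is undefined. On its natural reading as cumulative hours, intubation cuts it short, and the dose model is then biased toward more hours, fewer intubations under no effect. The false-benefit rate among proned patients runs from about 3% (one 2-3 h session) through about 30% (day 1 only) to over 90% (2 days) and 100% (5 days). The governing quantity, course length, is not in the protocol, and the number proned, the risk and the daily hours are assumed too. The direction is less certain if non-proned patients are included. This does not by itself invalidate the main yes/no comparison. It should be fixed.

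**What to change.** 1. Add to the collection form the date and time of first prone start and of intubation, and awake-prone hours in a fixed early window (for example the first 24 h from first prone start).
2. Fit the dose model among proned patients still un-intubated at the end of that window, with later intubation as the outcome and initial SpO2/FiO2 as a covariate.
3. Report total prone hours descriptively only, and keep them out of the model chosen by R2 and AIC.
4. State which hours column is awake, pre-intubation time, and keep any post-intubation hours out of the model.

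The cost is a few extra fields per chart and reworded analysis text. Patients intubated within the window (about 13 to 24 of 184 under the assumptions above) leave the dose analysis only and stay in the yes/no comparison, which this fix does not change. The dose result remains observational, and adjustment for initial SpO2/FiO2 may not remove all confounding by severity.

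### The adjusted prone effect is left to a model chosen by best R2 and AIC, which can drop prone, exaggerate a small effect or under-adjust it; the crude relative risk and its test are unaffected

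*Protocol*

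**What the plan says.** The main objective is an association: "To analyze the relationship between the awaken prone positioning and the need for orotracheal intubation". The Statistical analysis section approaches it in two layers.

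- **Crude layer.** Prone (yes/no) against intubation is tested first, by "Fisher's exact test or (> 5) Chi square test", at p < 0.05. The effect measure is given as: "Relative risk will be performed with a 95% confidence interval of significance (95% CI) and contingency tables".
- **Regression layer.** The plan then fits "linear regression models with the different variables: prone time, age, gender and orotracheal intubation, SpO2 / FiO2 index". The purpose it gives for these models is explanatory, namely to account for "their interactions (if the time in prone, age or gender affects the main objective"). A second purpose is added before the sentence ends: "adopting the best model that matches the observations (best R2, AIC) as a predictive model".

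The section does not say which criterion decides when R2 and AIC disagree, whether R2 is adjusted, or whether prone or any covariate must stay in. It ties no CI to the regression. Comorbidities are declared under Confusing variables ("Registration in the clinical record of any of the comorbidities described"), as is pharmacotherapy, but neither is on the regression list.

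**The concern.** The Methodology section describes a retrospective, comparative cohort, so the crude relative risk may partly reflect who was placed prone. The regression is the only planned analysis that takes age, gender or oxygenation into account. If fit decides its content, three things can happen to the adjusted prone effect:

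- it disappears, because prone did not improve AIC enough in this sample;
- it is exaggerated, because prone stays mainly when its estimate happens to be large;
- it is under-adjusted, because a covariate that predicts intubation weakly but differs between prone groups is removed.

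The usual CI from a selected model allows for none of this. The two criteria also pull apart: unadjusted R2 cannot fall when a term is added, whereas AIC charges for each term. An analyst who sees both has a free choice of model.

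**Working it through.** **1. The plan's own figure.** The Protocol gives no figure for the regression; its only one is the sample size. With N = 8463, z = 1.96, p = q = 0.5 and E = 0.05:

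n = N z² pq / [(N − 1)E² + z² pq] = 8463 × 0.9604 / (8462 × 0.0025 + 0.9604) = 8127.9 / 22.115 = 367.5, rounded up to 368.

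This reproduces. It is a precision calculation for one proportion and names no prone effect, so it does not rule out small effects.

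**2. Analytic check of AIC.** AIC drops a one-parameter term when its likelihood-ratio chi-square is below 2.

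- No true effect: P(chi-square on 1 df < 2) = 0.843, so prone is kept in 15.7% of data sets. A 95% CI excludes zero in 5%, and all of those lie among the kept ones. Coverage when kept is therefore about 1 − 0.05/0.157 = 68%, even with no confounding.
- True difference −5 points, assuming 184 per group and 35% risk without prone: SE = √[(0.35 × 0.65 + 0.30 × 0.70)/184] = 0.0488 and d = 0.05/0.0488 = 1.03. P(drop) = Φ(1.414 − 1.03) − Φ(−1.414 − 1.03) = 0.64.
- The same formula gives 0.24 at −10 points and 0.03 at −15 points.

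**3. Simulation.** Linear regression of intubation on every subset of prone, age, gender and SpO2/FiO2, with n = 368 and 1,500 data sets per scenario. Assumed, not from the Protocol:

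- baseline risk 35%, and about half the patients prone;
- risk changes of 0.04 per SD of age and 0.02 for gender;
- SpO2/FiO2 effect of −0.03, −0.06 or −0.10 per SD;
- SpO2/FiO2 related to prone at 0.8 log-odds per SD.

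Prone is yes/no here, standing in for prone time. Ranges run over the three SpO2/FiO2 strengths; effects are in percentage points.

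| True difference | AIC drops prone | Mean estimate when kept | Coverage when kept | Fixed full model: mean | Fixed full model: coverage |
|---|---|---|---|---|---|
| 0 | 83% | −0.7 to −1.8 | 59-71% | −0.2 to 0.1 | 95.1-95.7% |
| −5 | 62-66% | −10.0 to −10.5 | 86-91% | −4.8 to −5.0 | 94.3-95.1% |
| −10 | 24-27% | −12.2 to −12.9 | 93-96% | −9.9 to −10.3 | 93.5-94.3% |
| −15 | about 5% | −15.2 to −16.1 | 95-97% | −14.7 to −15.0 | 93.8-94.3% |

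A second simulation (same n and baseline risk, three modest confounders, 3,000 data sets per effect size) agrees. At −5 points prone was dropped in 70%; when kept, the mean was −9.8 points and coverage 86%. At 0, prone was kept in 17%, with 60% coverage when kept.

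**4. Unconditional error.** With no true effect, 17% × 40% = 6.8% of all data sets give a CI that wrongly excludes zero (second simulation). The first gives 4.9-7.1%. The nominal figure is 5%.

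**5. Covariates.** AIC dropped SpO2/FiO2, a true confounder here, in 54-59% of data sets when its effect was weak, 12-18% when moderate and under 1% when strong. With prone forced in and only the covariates selected, coverage was 92-95% and the mean was within 0.8 points of the truth.

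**6. The criteria against each other.** Unadjusted R2 returned the full model in 100% of data sets, as it must. Adjusted R2 did so in 5-28%.

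**The case against.** The strongest reply is that selection does not touch the planned main result. The hypothesis is tested by Fisher or chi-square, and the only prone effect with a promised 95% CI is the contingency-table relative risk. That is right. A reader might infer that the trial's reported prone effect and CI are distorted; the Protocol does not support this, because it promises no CI for a regression coefficient.

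Second, the sentence can be read as two separate tasks, with R2 and AIC governing only the predictive one, for which AIC is an ordinary choice. The wording allows this, but it names no other rule for the explanatory models, so the ambiguity itself needs removing.

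Third, it is tempting to say that R2 always picks the largest model. That holds only for unadjusted R2, and the Protocol does not say which it means.

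Fourth, coverage of 60-70% sounds like an error rate but is conditional on prone being kept. Over all data sets the false exclusion of zero is only a little above nominal at worst. Loss of weak confounders also did little harm under these assumptions; most of the damage comes from letting prone itself be selected.

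Fifth, prone time accrues after admission, so one might say that it cannot serve as a predictor. The Protocol never says that prediction is to be made at admission, so that criticism is not pressed.

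Finally, a SAP may exist. It could settle details, but the selection rule is stated in the Protocol and is open to comment as it stands.

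**Conclusion.** The point holds for the adjusted association and should be corrected; the crude analysis stands apart from it. One sentence gives the same regression models an explanatory and a predictive purpose, under two criteria that can disagree, with nothing protected from removal.

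The size depends on the true effect. At −5 points, AIC loses prone in most data sets and roughly doubles the estimate when it stays. At −10 points, coverage is near nominal but the retained estimate is still 2 to 3 points too large. At −15 points little is left of the problem.

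All of this rests on an assumed 35% baseline risk, the assumed covariate effects and a yes/no exposure; the Protocol gives none of these rates. The near-nominal coverage of the fixed model also assumes no confounders beyond those simulated. The comorbidities that the Protocol itself declares as confounders are outside the candidate list, so under-adjustment would remain even if every listed variable were kept.

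**What to change.** Split the sentence in two.

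1. **Association.** Take the adjusted prone-intubation effect and its 95% CI from one pre-specified model. Prone, age, gender, admission (pre-prone) SpO2/FiO2 and the comorbidities listed under Confusing variables stay in whatever their p-value, R2 or AIC. State whether prone enters as yes/no or as hours, and whether pharmacotherapy, listed in the same table, is included.
2. **Prediction, if wanted.** Confine R2/AIC selection to a separate model labelled predictive. Say which criterion decides and whether R2 is adjusted, and correct the reported fit for optimism, for example by bootstrap. Do not interpret its prone coefficient as the effect of prone.

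The cost is a change of wording, one bootstrap run and a slightly wider CI if a covariate proves unneeded. Entering the eight comorbidity categories separately would bring the association model to 4 + 8 = 12 terms, against about 368 × 0.35 = 129 intubations at the assumed baseline risk, so their coding should be fixed in advance too.
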